The decrease of pain sensitivity started at the 4th session for patients treated with neural mobilization only (MOB) and from the 5th treatment session for the patients using medicament plus therapeutic treatment group (MOB + MED). The improvements remained until the end of the treatment (Figure 3).

EVA was 1.5 for MOB group and 2.6 for MOB+MED thirty days after the end of the sessions. Control group (CONTROL), composed of individuals without any kind of pain or injury and who were treated with the neural mobilization technique, it was noted pain intensity on the VAS scale remained at zero until the follow up evaluation (Figure 3).

It should be mentioned that it was not possible to observe a statistically significant difference between the MOB and MOB + MED groups, which suggests that the Neural Mobilization technique alone can improve the pain of these individuals, and it could be considered an adjuvant therapy to the drug treatment of patients (Figure 3).

Roland-Morris Disability Questionnaire (RMDQ):

By adding the yes answers and reaching a value equal to or lower than 10 points, it shows that the person with low back pain presents without some kind of disability, that is, despite the pain, there is no impeding the accomplishment of their daily life tasks. However, if the total varies between 11 and 14 yes / indicated alternatives, it indicates a mild or moderate inability of this individual to perform their daily activities. When the positive responses are equal to or greater than 15, it indicates that this individual has a severe disability [12].

In the MOB group, 17 individuals were evaluated. In the initial measurement, we observed that 15 individuals presented in the normal parameter, not showing any kind of incapacity in performing daily life activities. Two individuals from the same group, presented, in the initial measurement, a severe incapacity to perform the activities of daily living. At the end of the treatment, this questionnaire was reapplied, and 16 of the subjects presented normal parameters, and one of the individuals with severe disability returned to normal levels; the other individual who also presented a severe level of disability, partially reversed their condition, going to mild/moderate disability when performing activities of daily living (Table 2).

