In the MOB + MED group, eleven individuals were evaluated. In the initial measurement, we observed that 6 individuals presented in the normal parameter; 3 subjects had mild / moderate disability and 2 individuals from the same group, presented, in the initial measurement, a severe incapacity to perform the activities of daily living. After the end of the treatment, the questionnaire was reapplied, and 9 of the individuals presented in the normal parameter. Three of the individuals with some degree of disability, returned to normal levels

and only 2 individuals who had a severe level of disability did not improve their disability when performing activities of daily living (Table 2).

In the control group (CONTROL), composed of 5 healthy individuals, with no complaints of low back pain and without injury, initially they had normal parameters, and did not present any type of disability when performing daily life activities, after the application of the proposed protocol (Table 2).

The Oswestry Disability Index (ODI):

In the initial measure (I) of the ODI were assessed after the application of the mathematical formula to evaluate the level of incapacity of the individuals. The first application of ODI can be classified into five levels of disability. The first stage classified in 0-20%, characterizes a minimal disability. The second stage in the range of 21-40%, characterizes a moderate disability. Followed for the range of 41-60%, that characterizes an intense disability. The range of 61-80% characterizes an immobilization. And finally, the range of 80-100%, that means invalidity.

The Final measure (F) of the ODI assessed was the effect of the treatment in the evolution of the clinical condition after the appliance of the mathematical formula. The first stage classifies the evolution in excellent in the range of 0-20%. The range of 21-40% classifies the evolution in great. The range of 41-60%, classifies the evolution in maintenance. The range of 61-100%, classifies the evolution after the treatment as worse.

Comparing the initial and the final measure of the ODI, it can be observed an improvement of the clinical condition of the subjects assessed in both groups, MOB, and MOB+MED. Only the CONTROL group maintained the same results in both measures (Table 3).

Lumbar mobility:

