Regarding the Roland-Morris Disability Questionnaire (RMDQ) and Oswestry Disability Index (ODI), we also used to analyze the level of physical disability induced by low back pain in each study volunteer. In our work, we can suggest that the protocol proposed was able to improve the disability of individuals treated only with the neural mobilization technique from mild to normal in almost all patients in RMDQ. It should be mentioned that the individuals treated with the combination of medicaments had a higher level of disability than the patients that received only MOB treatment in RMDQ.

In RMDQ, the results obtained so far in this questionnaire suggest that the protocol proposed in this study was able to aid in the improvement of the mild and moderate disability of individuals treated only with the neural mobilization technique and also associated with drug treatment. It should be mentioned that the individuals treated with the combination of treatments (MOB + MED group) had a higher level of disability than the MOB group.

We could also observe an improvement in the individuals' disability through ODI, comparing before and after the technique, where the subjects treated with MOB only had a lower level of disability compared to the MOB + MED group, both of which obtained a reduction of the level of disability after the application of the proposed protocol.

Based on both questionnaire applied in this study, we could demonstrate their success in improving the quality of life from all patients analyzed in this program.

This technique proves to be a possible adjunct therapy to the drug treatment, since it has no side effects, and may help in reducing the dose and administration period of the medication. In addition to improving their functional capacity and quality of life, thus demonstrating their importance for clinical practice.

CONCLUSION:

In summary, we can affirm that the technique chosen for the treatment of individuals with chronic low back pain, with or without irradiation to one of the lower limbs, was effective in reducing the pain intensity of these patients when comparing the initial with the final evaluation, as well as between treatment sessions.

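### The final ODI is graded as change without using baseline, and the Discussion's RMDQ claims for the technique-only group contradict the reported counts

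*Combined protocol and SAP*

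**What the plan says.** All references are to the combined protocol and SAP.

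**ODI (Results, Oswestry Disability Index).** At the initial measure the percentage is a disability level: "The first stage classified in 0-20%, characterizes a minimal disability", and so on up to invalidity. At the final measure the same percentage becomes a grade of clinical evolution: "The first stage classifies the evolution in excellent in the range of 0-20" per cent, then "The range of 21-40% classifies the evolution in great", then maintenance for 41-60% and worse for 61-100%. The section goes on to compare initial with final and finds improvement in MOB and MOB+MED; "Only the CONTROL group maintained the same results in both measures".

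**RMDQ (Results, Roland-Morris).** A score of 10 or less is normal, 11 to 14 is mild/moderate, and 15 or more is severe. For the 17 MOB patients assessed at baseline, "we observed that 15 individuals presented in the normal parameter" and two were severe. At the end 16 were normal; one severe patient had become normal and the other had "partially reversed their condition, going to mild/moderate disability". In MOB+MED (11 assessed), three patients returned to normal and "only 2 individuals who had a severe level of disability did not improve their disability".

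**Discussion.** Disability in technique-only patients is said to have gone "from mild to normal in almost all patients in RMDQ". The next paragraph again credits the technique, alone as well as with drugs, with helping mild and moderate disability. A later sentence claims, from both questionnaires, better quality of life in every patient analysed.

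**The concern.** A grade of change has to depend on where the patient started, and the final-ODI grade does not. A patient who stays at 0-20% is excellent, and one who worsens from 0-20% to 21-40% is great. A fall from 80% to 61% would be worse (hypothetical here, since nobody ends above 60%). A reader who applies the labels to Table 3 would count unchanged people as successes.

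The RMDQ sentences are a matter of fact. They describe a move from mild to normal in a group with nobody in the mild/moderate band at baseline. Functional capacity is one of the stated aims, and the two questionnaires are the patient-reported evidence closest to it, so a false account of them misstates what the technique alone was seen to do.

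**Working it through.** **1. RMDQ counts.** Inputs: the Roland-Morris text in Results, and Table 2. The severe cell of the initial MOB row is not readable in the text available to me, so that value is taken from the Results text; I do not count this as an error.

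| Group | Time | Normal | Mild/moderate | Severe | n |
|---|---|---|---|---|---|
| MOB | Initial | 15 | 0 | 2 | 17 |
| MOB | Final | 16 | 1 | 0 | 17 |
| MOB+MED | Initial | 6 | 3 | 2 | 11 |
| MOB+MED | Final | 9 | 0 | 2 | 11 |

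The document's own final count is reproduced: 15 already normal + 1 from severe = 16, and 16 + 1 mild/moderate = 17. From these counts:

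- MOB, mild/moderate at baseline: 17 − 15 − 2 = 0, so moves from mild/moderate to normal are 0/17.
- MOB, already normal: 15/17 = 88%.
- MOB, changed band: 2/17 = 12%, both from severe.
- MOB+MED, mild/moderate to normal: 3/11 = 27% (6 + 3 = 9 normal at the end).
- MOB+MED, still severe: 2/11 = 18%.

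All three moves from mild/moderate to normal were therefore in MOB+MED.

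**2. ODI bands.** Input: Table 3.

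| Group | Time | 0-20 | 21-40 | 41-60 | 61-80 | 80-100 | n |
|---|---|---|---|---|---|---|---|
| MOB | Initial | 7 | 7 | 1 | 1 | 0 | 16 |
| MOB | Final | 14 | 1 | 1 | 0 | 0 | 16 |
| MOB+MED | Initial | 0 | 8 | 3 | 0 | 0 | 11 |
| MOB+MED | Final | 7 | 2 | 2 | 0 | 0 | 11 |
| CONTROL | Initial and final | 5 | 0 | 0 | 0 | 0 | 5 |

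The table gives margins only, so individual change can be bounded but not determined. The bounds are the minimum and maximum over every initial-by-final table with these margins.

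*MOB.* Only 1 + 1 = 2 patients end outside 0-20%. Of the 7 who began in that band, at least 7 − 2 = 5 and at most 7 stayed. Those who moved into it number 14 − 7 = 7 to 14 − 5 = 9. Patients improving at least one band: 7 to 9 of 16. Patients worsening: 0 to 2.

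*MOB+MED.* Nobody began in 0-20%, so all 7 who ended there moved in. The 2 who ended at 41-60% cannot have improved a band, because nobody began above 60%. The 2 who ended at 21-40% may or may not have come from 41-60%. Patients improving a band: 7 to 9 of 11. Not improving a band: 2 to 4 of 11.

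*CONTROL.* 5/5 unchanged.

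**3. The labels applied to Table 3.** CONTROL would be 5/5 excellent with no change. MOB would be 14/16 excellent, of whom 5 to 7 were already in that band. The MOB margins also allow a patient to improve from 61-80% to 41-60% and be graded maintenance, or to worsen from 0-20% to 21-40% and be graded great.

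**4. Completeness.** Pain patients: 18 + 12 = 30. RMDQ: 17 + 11 = 28, so 2 are missing. ODI: 16 + 11 = 27, so 3 are missing. Results state that all 35 participants were analysed; with the 5 controls the questionnaire totals are 33 and 32.

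**The case against.** The ODI labels affect no reported result. No count of them is given, Table 3 already uses one set of percentage columns at both times, and the text rests its claim on comparing initial with final. That is correct: the fault lies in the labels, and the printed shift does not depend on them.

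On the RMDQ, almost all MOB patients did end normal (16/17), and scores may have fallen within the 0-10 band, which band counts cannot show. The second Discussion sentence also covers MOB+MED, where all three mild/moderate patients became normal. These points stand, but they do not rescue a statement that MOB patients began as mild: 15 of the 16 who ended normal had begun normal.

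On quality of life, Materials and Methods itself speaks of a quality of life questionnaire, so the term has a source in the document, although the RMDQ is then described there as a measure of physical disability. The reference to all patients fails under either term.

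Finally, the document does not say which instruments measure functional capacity; treating the questionnaires as such is a reasonable inference. The contradictions do not depend on it.

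**Conclusion.** The concern holds. The final-ODI grades claim to describe change but are read from the final score alone. They would grade as excellent 5/5 unchanged controls and 5 to 7 MOB patients who never left the lowest band. The RMDQ statement about technique-only patients is false as a band change: 0/17, against a claim of almost all. The claim about all patients is contradicted by 2/11 MOB+MED patients who remained severe on the RMDQ and by 2 to 4 of 11 who did not improve an ODI band.

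The reach is limited. The ODI shift (MOB 7 to 14 of 16; MOB+MED 0 to 7 of 11) remains, both severe MOB patients improved on the RMDQ, and the VAS results, the lumbar mobility results and the Conclusion do not rest on these statements. The ODI figures assume that the Table 3 counts are as printed; the initial and final rows agree on 16 and 11, but no text confirms them. Change within a band is not visible for either questionnaire.

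**What to change.** - Delete the evolution labels, keep the disability bands at both times, and add an initial-by-final cross-tabulation for each group.
- For each pain group, report the paired change in ODI percentage and in RMDQ total (0-24) with a 95% confidence interval, using the within-group paired method already named in Materials and Methods. Results and Tables 2 and 3 give only band counts for both questionnaires.
- State that these analyses are complete-case (RMDQ: MOB 17 of 18, MOB+MED 11 of 12; ODI: MOB 16 of 18, MOB+MED 11 of 12) and explain the missing questionnaires.
- Replace both RMDQ sentences in the Discussion with: *15 of 17 MOB patients were already in the normal RMDQ band; the 2 with severe disability each improved, one to normal and one to mild/moderate; in MOB+MED 3 of 11 moved from mild/moderate to normal and 2 of 11 remained severe.*
- In the sentence on quality of life, refer to disability and remove the reference to all patients. The following paragraph repeats the quality-of-life claim and should be aligned.

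The cost is a cross-tabulation, a small paired analysis of data already collected, and a few reworded sentences. The RMDQ account of MOB becomes less favourable; the ODI shift does not change. The missing questionnaires (2 of 30 for RMDQ, 3 of 30 for ODI) can be disclosed but not recovered by re-analysis.

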Figure 4: Lumbar spine mobility before (I = Initial Measure) and after (F = Final Measure) treatment. The symbols represent the statistical significant difference between times analyzed (* p<0.0001 between final measure (F) and initial (I) in MOB group; # p<0.05 between final measure (F) and initial (I) in MOB + MED group).

Table 1: Characterization of the participants of the study in each group.

Table 2: Analysis of results obtained in the initial (I) and final (F) measurements on the Roland-Morris Disability Questionnaire in MOB, MOB + MED and CONTROL groups, before and after the proposed treatment.

Table 3: Analysis of results obtained in the initial (I) and final (F) measurements on the Oswestry Disability Index in MOB, MOB + MED and CONTROL groups, before and after the proposed treatment.

Table 1:

GROUPS:		Control group	MOB group	MOB + MED group
Main age (yr)		28,4±11,5	43,4±13,9	43,3±15,0
Gender	M	2	7	5
	F	3	11	7
Education	Elementary	0	0	2
	High school	4	12	9
	University	1	6	1
	Not Finished	0	0	0
Ocupation Status	Full-time Worker	1	10	1
	Part-time Worker	1	7	3
	Unemployed	0	0	3
	Retired	0	1	1
	Disabled	0	0	3
	Student only	3	0	1

Table 2:

Roland-Morris Disability Questionnaire (RMDQ)						
Group-time	0 a10 - Normal	11 a 14 – Mild/Moderate desability	15 a 24 – Seevre disability			
MOB - I	15	0				
MOB -F	16	1	0			
MOB+MED - I	6	3	2			
MOB+MED - F	9	0	2			
Control – I	5	0	0			
Control – F	5	0	0			

Table 3:

Oswestry Disability Index (ODI)							
Group - Time	0-20%	21-40%	41-60%	61-80%	80-100%		
MOB - I	7	7	1	1	0		
MOB -F	14	1	1	0	0		
MOB+MED - I	0	8	3	0	0		
MOB+MED - F	7	2	2	0	0		
Control – I	5	0	0	0	0		
Control – F	5	0	0	0	0		

Figure 1:

Figure 2:

[figure not shown]

Figure 3:

[figure not shown]

Figure 4:

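### The final-ODI 'evolution' scale grades where a patient ends, not how far the patient has changed, because the initial score does not enter it

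*Combined protocol and SAP*

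**What the plan says.** The rule is in the combined protocol and SAP, RESULTS, under The Oswestry Disability Index (ODI). The initial ODI is sorted into five levels of disability. The final ODI is given a different purpose: "The Final measure (F) of the ODI assessed was the effect of the treatment in the evolution of the clinical condition". Four grades follow, each tied to a range of the final percentage. For the lowest scores the text reads "The first stage classifies the evolution in excellent in the range of 0-20" per cent. Scores of 21-40% are called great and scores of 41-60% maintenance. For the highest scores it reads "The range of 61-100%, classifies the evolution after the treatment as worse".

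No change score, baseline adjustment or minimum improvement is mentioned. The same range therefore has two meanings: 21-40% is moderate disability at entry and a great evolution at the end.

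Table 3 gives initial (I) and final (F) counts in the same five numeric bands for all three groups, without the evolution labels. The section then compares the two measures, reports improvement in MOB and MOB+MED, and says of the healthy group: "Only the CONTROL group maintained the same results in both measures (Table 3").

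**The concern.** A scale said to describe evolution should give a better grade to a patient who improved than to one who did not. This one cannot, because two patients with the same final score receive the same grade whatever their starting points. Taken literally, and with invented score pairs, a patient going from 2% to 38% is graded great, one going from 78% to 62% is graded worse, and a healthy control who stays in the lowest band is graded excellent.

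The grades would therefore largely reflect how disabled people were at entry. The two patient groups differ sharply there: 7 of 16 MOB participants began in 0-20%, but none of the 11 in MOB+MED did ("MOB+MED - I 0 8 3 0 0"). If the labels were used to summarise response, or to compare the groups, the less disabled group would have an advantage before any treatment was given. Functional capacity is among the stated aims of the combined document, and the ODI is one of the two disability questionnaires on which its Discussion relies.

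**Working it through.** **Inputs (Table 3; bands 0-20, 21-40, 41-60, 61-80, 80-100%)**

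| Group | Initial | Final | n |
|---|---|---|---|
| MOB | 7, 7, 1, 1, 0 | 14, 1, 1, 0, 0 | 16 |
| MOB+MED | 0, 8, 3, 0, 0 | 7, 2, 2, 0, 0 | 11 |
| Control | 5, 0, 0, 0, 0 | 5, 0, 0, 0, 0 | 5 |

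The plan gives no figure of its own for these grades, so there is none to reproduce.

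**Step 1. Grades if nobody changed band.** Apply the final-measure labels to the initial counts. Excellent or great = count in 0-20% + count in 21-40%.

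- MOB: 7 + 7 = 14 of 16 (87.5%)
- MOB+MED: 0 + 8 = 8 of 11 (72.7%)
- Back-pain patients: 14 + 8 = 22 of 27 (81.5%)
- With controls: 22 + 5 = 27 of 32 (84.4%)

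**Step 2. Grades from the final counts.**

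- MOB: 14 + 1 = 15 of 16
- MOB+MED: 7 + 2 = 9 of 11
- Back-pain patients: 15 + 9 = 24 of 27 (88.9%)
- With controls: 24 + 5 = 29 of 32 (90.6%)

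**Step 3. The top grade alone.**

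- No change: 7 + 0 = 7 of 27 patients (25.9%); with controls 12 of 32
- Final: 14 + 7 = 21 of 27 patients (77.8%); with controls 26 of 32

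The two favourable grades together hardly distinguish the no-change case from the final result (22 against 24). The top grade does (7 against 21).

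**Step 4. Excellent grades that involve no change of band.** Assume the same 16 MOB participants at both times. Those starting outside 0-20% number 7 + 1 + 1 = 9, and 14 finished inside it. So at least 14 - 9 = 5 of the 14 were already in that band at entry. All 5 controls were too ("Control – I 5 0 0 0 0").

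**Step 5. What the Table 3 totals leave open.** Again assume the same people at both times.

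- MOB: only 1 + 1 = 2 people finished outside 0-20%, so at most 2 moved to a worse band.
- MOB+MED: nobody started in 0-20%, so only the 2 who finished in 41-60% could have moved to a worse band.
- In both groups, zero is also compatible with the counts.

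Between 0 and 4 of 27 patients may thus have worsened by a band. Neither the table nor the labels can say which. A MOB participant ending in 41-60% is graded as maintenance whether that person started higher, lower or in the same band.

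**Step 6. Missing ODI rows.** Group sizes are 18, 12 and 5 (35 in all); the ODI rows total 32. The 3 absent are back-pain patients. Counting them, the no-change figure lies between 22 and 25 of 30 patients (73.3% to 83.3%), or 27 to 30 of 35 overall (77.1% to 85.7%).

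**The case against.** The strongest reply is that the labels are never used. No count of excellent, great, maintenance or worse appears anywhere. Table 3 uses the same five bands at both times, and the ODI conclusion, repeated in the Discussion, is an initial-versus-final comparison. The controls are described as unchanged, not as having evolved excellently. No between-group comparison of the grades is made. All of this stands, and it limits the consequence.

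Three stronger readings are tempting but not supported:

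- **That the reported ODI improvement is a product of the scale.** It is not. The 0-20% band rises from 7 to 14 in MOB and from 0 to 7 in MOB+MED. With the same people measured twice, at least 7 in each group moved into it.
- **That only 2 of the 29 favourable grades go beyond what no change would give.** The subtraction is right (29 - 27), but it merges two grades that the rule keeps apart and counts healthy controls. On the top grade alone, the excess among patients is 21 - 7 = 14.
- **That improvers were in fact graded worse.** The rule allows it, but no final score lies in 61-100%, and only one participant started there.

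It can also be said that the methods already name a paired t test for within-group differences. That would be a proper analysis of change, but the ODI section reports no mean change, interval or p-value. The evolution scale is the only interpretive rule written for the final ODI.

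**Conclusion.** The point holds as a defect in the outcome definition. The scale is presented as grading evolution under treatment, but it grades end status. With no change of band it would still place 22 of 27 back-pain patients in the two favourable grades, against 24 of 27 at the final measure, and at least 5 of the 14 MOB participants in the top grade were there at entry. It does not overturn the before-after shift shown in Table 3.

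Assumptions: the reference case is that every person stays in the initial band, which is not the same as everything that could happen under an ineffective treatment. The minimum of 5 and the range of 0 to 4 require the same participants in the initial and final rows. The three patients absent from Table 3 are outside the main counts.

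Severity is moderate. The Protocol, under Calculation of the sample, names the VAS as primary end point, and the ODI is absent from that document's outcome measures.

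**What to change.** - Delete the final-score evolution scale from the ODI section.
- Define the ODI outcome as each patient's final minus initial percentage score, a negative value meaning less disability.
- Report the mean change with a 95% confidence interval separately for MOB and MOB+MED, with the number of patients contributing (16 of 18 and 11 of 12 on present counts).
- Using the five bands of Table 3 at both times, report how many patients in each group moved to a better band, stayed, or moved to a worse one. This settles what Step 5 leaves open.
- Leave the healthy controls out of any count of improvement, since all five start in the best band.

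The cost is re-tabulation of scores already collected at both evaluations. No new data are needed.

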Thirty-five individuals volunteers participated in this study, with a mean age of 49.64 years, were 21 women and 14 men. After being selected, the volunteers were allocated to three groups: Neural Mobilization Group (MOB), consisting of individuals with low back pain and treated with the technique, with a total of 18 participants; Neural Mobilization + Medication Group (MOB + MED), constituted by individuals with low back pain, who underwent the mobilization technique associated with medication, a total of 12 participants; and the control group (CONTROL) constituted by healthy individuals without any kind of injury or pain complaint who received the application of the neural mobilization technique, with a total number of 5 participants.

After fulfilling the eligibility criteria, a clinical evaluation and assessments of pain and mobility were carried out, and a quality of life questionnaire was applied (details below).

In order to preserve the accuracy of the intervention effectiveness, participants who missed more than two sessions were excluded from the study. All subjects were assessed by a blinded evaluator. Both participants and evaluator were encouraged not to discuss the received intervention.

First, all personal data from each subject were obtained. Age, body mass, height, profession, school education. After this first step, the participants were submitted to two evaluations, prior to and at the end of the therapeutic program. Both to assess the pain

intensity and to assess the mobility of the lumbar spine, as well as the application of a quality of life questionnaire. A follow up was done thirty days after the end of the treatment to verify the effect of the protocol after the patients return to the normal daily life activity. A characterization and physical examination card were used for a better analysis of the volunteers. The subjects in all three groups were submitted to the same evaluation protocol.

A visual analogue scale (VAS) was used for the assessment of pain intensity, which consists of a line ranging from 0 to 10, where zero characterizes absence of pain and ten, worst pain. After clarifying how to complete the scale, the volunteer was asked to mark a point on the line that indicated the intensity of pain that he or she was feeling at moment of the evaluation [9].

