The Portuguese version of the Roland - Morris Disability Questionnaire (RMDQ) [10] was applied to the subjects of the study. The questionnaire consists in assessing the severity and level of physical disability induced by low back pain through 24 alternatives with dichotomic answers (yes or no). The questionnaire must be self-filled by the volunteers, demonstrating their success or difficulty in performing their daily life tasks associated with their pain, and the final result of the questionnaire is the sum of the yes or the marked responses. As some patients had some difficulty reading or understanding the instructions of the questionnaire, the reading was done together with the researchers.

It was applied the Oswestry Disability Index (ODI) version 2.0, validated in 2007 by Vigatto et al [11]. The scale consists on a list of ten questions with six possible answers, each answer has a score ranging from 0 to 5, in the order in which they are listed, that is, the first value is 0 and the last value is 5. The first question assesses the intensity of the pain and the others assess the effect caused by the pain on the performance of activities of daily living, like personal cares, dress up, sleep and so forth [12].

To analyze the total score obtained in this questionnaire, there is a mathematical formula that can be used. After adding all the results marked by the individuals in the questionnaire were used a mathematical formula to calculate the total score obtained in percentage for each volunteer. The total score is divided by the number of answered questions divided by 5. The result of this division is multiplied by 100 and the final values are given in percentages, thus ([score \div (number of answered questions X 5)] X 100)[12].

In order to evaluate the mobility of the lumbar spine, the 3rd finger to the ground distance test was used. This test consists of an active test, where the individual is placed in an orthostatic position, with the feet separated in the hip line, keeping knee extended and heel leaning on the ground, then the participant is asked to perform a trunk flexion with the arms extended and try to bring his hand closer to the ground. Then, using a tape measure, the

distance between the tip of the 3rd finger and the ground is measured, and the value given in centimeters (cm) is considered as the mobility of the volunteer lumbar spine [13] [14].

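### The Discussion reports improved quality of life on the strength of two disability scales; a quality-of-life questionnaire is announced, but none is named, described or reported

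*Combined protocol and SAP*

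**What the plan says.** In the combined protocol and SAP, Materials and Methods says that after eligibility "a quality of life questionnaire was applied (details below". The account of the initial and final evaluations mentions it again: "as well as the application of a quality of life questionnaire". Two questionnaires are then described. Of RMDQ the text says: "The questionnaire consists in assessing the severity and level of physical disability induced by low back pain". Of ODI it says that the first item rates pain intensity and "the others assess the effect caused by the pain on the performance of activities of daily living".

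The Results use ODI "to evaluate the level of incapacity of the individuals" and grade it in five levels of disability. The Discussion says of RMDQ and ODI together: "we also used to analyze the level of physical disability induced by low back pain in each study volunteer".

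Later in the Discussion the wording changes. One sentence, about everyone in the treatment programme, reads: "Based on both questionnaire applied in this study, we could demonstrate their success in improving the quality of life from all patients analyzed in this". The paragraph after it ends: "In addition to improving their functional capacity and quality of life, thus demonstrating their importance for clinical practice".

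The Method section of the separate protocol also states that a quality-of-life questionnaire was administered and promises details. Its Outcome measures section covers VAS, finger-to-ground distance, goniometry and cytokines, and describes no questionnaire.

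**The concern.** Disability from back pain and quality of life are different outcomes. They may be related, but a change in one does not measure a change in the other unless the instrument has been shown to capture both. The documents offer no argument or validation for reading RMDQ or ODI as a quality-of-life measure, and their own definitions point to disability.

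What is at stake is a stated benefit. The Discussion presents better quality of life as demonstrated, lists it beside functional capacity, and uses it to argue for clinical importance. A reader would take away an effect on an outcome for which no result under that name is shown. The extension to every patient goes further still, because it says that nobody failed to benefit.

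**Working it through.** No figure in the documents needs to be reproduced. The check has two parts.

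**1. Is a quality-of-life measure identified anywhere?**

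| Place | What it offers |
|---|---|
| Combined document, stated aim | Pain intensity and functional capacity; quality of life not named |
| Combined document, Methods | A quality-of-life questionnaire announced twice, unnamed; the only questionnaires described are RMDQ and ODI |
| Combined document, Results | VAS, RMDQ, ODI and lumbar mobility |
| Combined document, Tables 2 and 3 | RMDQ and ODI category counts |
| Combined document, Discussion | Both questionnaires called disability measures, then given as the basis for a quality-of-life benefit |
| Separate protocol | A quality-of-life questionnaire announced; no questionnaire described |

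No quality-of-life instrument, score or analysis appears under that name in either document.

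**2. If the two scales are taken at face value, did every patient improve?**

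Inputs are the Results text and Tables 2 and 3. The patient groups are MOB (18) and MOB + MED (12), so 18 + 12 = 30 patients with low back pain. The healthy controls are left out. The MOB severe count at the start (2) comes from the Results text, because that cell of Table 2 cannot be read in the copy available; this is not treated as an error.

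*RMDQ*

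| Group and time | Normal | Mild/moderate | Severe | Total |
|---|---|---|---|---|
| MOB, start | 15 | 0 | 2 | 17 |
| MOB, end | 16 | 1 | 0 | 17 |
| MOB + MED, start | 6 | 3 | 2 | 11 |
| MOB + MED, end | 9 | 0 | 2 | 11 |

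- Patients counted: 17 + 11 = 28 of 30.
- Already normal at the start: 15 + 6 = 21, or 21/28 = 75%.
- Moved to a better category: 2 in MOB (one from severe to normal, one from severe to mild/moderate) and 3 in MOB + MED, so 2 + 3 = 5, or 5/28 = 18%.
- Stayed severe: 2, both in MOB + MED.
- Check: 21 + 5 + 2 = 28.

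*ODI*

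| Group and time | 0-20% | 21-40% | 41-60% | 61-80% | Total |
|---|---|---|---|---|---|
| MOB, start | 7 | 7 | 1 | 1 | 16 |
| MOB, end | 14 | 1 | 1 | 0 | 16 |
| MOB + MED, start | 0 | 8 | 3 | 0 | 11 |
| MOB + MED, end | 7 | 2 | 2 | 0 | 11 |

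- Patients counted: 16 + 11 = 27 of 30.
- Lowest band: from 7 + 0 = 7 at the start to 14 + 7 = 21 at the end.
- In 41-60% at the end: 1 + 2 = 3. The Results' own key for the final measure labels that band as maintenance.
- The table gives totals and not each patient's path, but a bound follows. The 7 MOB patients who began in the lowest band could not move to a better one. Nobody in MOB + MED began above 41-60%, so the 2 who ended there stayed in their band or got worse. At least 7 + 2 = 9 of 27 therefore did not move to a better band, and at most 27 - 9 = 18 did.

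For both scales only category counts are reported, with no scores, changes in score or test results.

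**The case against.** The strongest reply is that the Discussion is open about its basis. It names the two questionnaires, their data are in the Results, and ODI asks about matters such as personal care and sleep that bear on daily well-being. A careful reader can see which scales are meant. The sentences are also Discussion remarks: neither the stated aim nor the section headed Conclusion mentions quality of life. This much stands. The statement does rest on data, but on disability data carrying another name. That limits the harm without making the label right.

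Three stronger readings are tempting, and the documents do not support them.

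- A reader might infer that quality of life was never measured. Both documents say that a quality-of-life questionnaire was given. The text fits either a mislabelling of RMDQ and ODI or a separate instrument that was not reported, and nothing in it decides between the two.
- A reader might infer that disability is counted twice, once as functional capacity and once as quality of life. The Discussion ties functional capacity to the finger-to-ground test, and the Conclusion ties it to pain and lumbar mobility. The quality-of-life statement is tied to the questionnaires.
- A reader might infer from the RMDQ counts that 21 patients gained nothing. A score can fall within the normal category, and counts cannot show that. They fail to demonstrate improvement in everyone, which is not the same as showing its absence in those 21.

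**Conclusion.** The point holds as a fault of reporting and of outcome definition. The Discussion states twice that quality of life improved, once for every patient analysed, and the only stated support is two scales that the same document defines as disability measures. No quality-of-life result can be computed from either document.

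The all-patients wording fails separately. On RMDQ, 5 of 28 counted patients moved to a better category and 2 remained severe. On ODI, at least 9 of 27 did not move to a better band. Two patients on RMDQ (30 - 28) and three on ODI (30 - 27) are not counted at all.

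The conclusion assumes that the published counts are correct and that RMDQ and ODI measure what the document says they measure. It leaves the reported pain and mobility results untouched. It does not show that quality of life failed to improve, or that no such questionnaire was completed.

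**What to change.** First settle whether a separate quality-of-life instrument was administered.

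- **If it was:** name it in the Method section of the protocol and in Materials and Methods of the combined document, describe its scoring, and report its results with the number of patients assessed. The Discussion can then rest its statement on those results.
- **If it was not:** in Materials and Methods of the combined document, replace both mentions of a quality-of-life questionnaire with disability questionnaires (RMDQ, ODI). Remove or correct the mention in the protocol. Delete both quality-of-life statements from the Discussion.

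In either case, drop the claim that all patients improved. State the questionnaire finding as the observed shift in disability categories with the number counted. For RMDQ: of 28 patients, 21 normal at the start, 5 moved to a better category, 2 stayed severe. For ODI: of 27 patients, the lowest band rose from 7 to 21, with 3 in 41-60% at the end. A change in mean score should not be stated from the present tables, because they hold only category counts.

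If no separate instrument exists, the change is to wording only. If one exists, its data must be tabulated and reported. The downside is a narrower stated benefit: disability in place of quality of life, and some patients in place of all.
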